2.3 Secondary Hypotheses and Objectives

Hypotheses

- H3. The incidence of cardiovascular disease in HIV-infected children is increased with EBV and CMV infections.
- H4. The incidence of lymphoproliferative interstitial lung disease in HIV-infected children is increased with EBV infection.
- H5. HIV associated abnormalities of cardiovascular anatomy or function in the fetus persist into the neonatal period.
- H6. Identifiable cofactors of HIV-infection are associated with alterations in cardiovascular anatomy and function in the neonatal infant and child and include:
 - a. Pulmonary/systemic bacterial/viral infection
 - b. Altered immune system
 - c. Primary treatment of HIV-infection
 - d. Perinatal events (including intrauterine growth retardation, drug exposure, or infection) and neonatal illness
 - e. Growth failure
- H7. Identifiable cofactors of HIV-infection are associated with specific pulmonary** complications in the neonatal infant and child and include:
 - a. Altered immune system
 - b. Primary treatment of HIV-infection
 - c. Perinatal events (including intrauterine growth retardation, drug exposure, or infection) and neonatal illness
 - d. Growth failure

Objectives

- 02. To determine whether pulmonary and cardiovascular disease associated with vertically transmitted HIV infection is detectable with sensitive diagnostic methods before clinical signs and symptoms appear.
- 03. To estimate the recurrence rate of PCP.
- 04. To determine whether PCP accelerates the rate of decline of lung function and shortens the life span of HIV-infected children with chronic lung disease.

* Specific cardiovascular complications related to these hypotheses for the fetus are a-h, and for the postnatal infant and child are b-i:

- a. Altered umbilical blood flow profile
- b. Structural heart disease
- c. Altered myocardial performance
- d. Pericardial effusion with and without hydrops
- e. Arrhythmias
- f. Altered chamber size and wall thickness
- g. Cardiac valvular insufficiency or obstruction
- h. Cardiac tumors or masses
- i. Endocarditis (active or healed)

** Specific pulmonary complications related to these hypotheses are:

- a. Upper respiratory infection (rhinitis, pharyngitis, otitis, sinusitis)
- b. Fungal pulmonary infection
- c. Viral pulmonary infection
- d. Bacterial pulmonary infection
- e. Mycobacterial pulmonary infection
- f. Pneumocystis carinii pneumonia
- g. Lymphoproliferative lung disease
- h. Other interstitial lung diseases

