4.2 Sample Size

An estimated 200 Group I and an estimated 600 Group II subjects are expected to be entered into the study. The actual sample size of the Group II population may exceed 600 since the objective of the study is to examine a population of infected children and the number to be recruited is dependent on the transmission rate of HIV infection from mother to child. The transmission rate is estimated to be around 20%. Therefore, it is expected that 120 Group IIa (HIV-positive) subjects will ultimately be diagnosed as positive. The remaining children recruited into the study will be classified as Group IIb (HIV-negative) subjects on the basis of negative HIV cultures at 6 months and confirmed serologically after passively acquired maternal antibodies are no longer present. It is estimated that there will be 480 Group IIb subjects, 200 of whom will be selected as controls for follow-up beyond the age of 6 months.

At the time the RFP was issued the transmission rate was thought to be 40%. At the conclusion of the protocol development the transmission rate appeared to be 30%. More recent findings indicate that the transmission rate is closer to 20%. The transmission rate utilized to determine HIV-positive status may continue to change as the HIV epidemic progresses and as findings of other scientific studies are reported in the literature.

Section 4.2.1 describes the randomization of Group IIb subjects. Section 4.2.2 gives the precision of estimating an incidence or prevalence for various sample sizes that may occur in the study for different groups or subgroups. Section 4.2.3 gives the sample sizes required to compare complication rates in HIV-infected and non-infected children (Groups IIa and IIb) for various complication rates in the two groups. These sample size estimates relate to the primary hypotheses and objectives.

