To determine whether diagnostic methods are able to detect cardiac or pulmonary disease before signs or symptoms appear in HIV-infected children (Objective O2), the sensitivity, specificity and positive and negative predictive values of each method will be determined. In order to determine the optimal cut-point for a diagnostic measure, a receiver operating characteristic (ROC) analysis will be performed (Metz, 1978). Combinations of diagnostic methods that may better detect disease will be evaluated using logistic regression analysis. The specific diagnostic methods likely to be of value are: LDH or PO_2 (or $A-aO_2$) for PCP, IgG for lymphoproliferative lung disease, echocardiogram measures (e.g., fractional shortening) for ventricular disease EKG measures (e.g., PR interval) for detecting arrhythmia, and DTPA for detecting early lung disease.

To evaluate whether PCP accelerates the rate of lung function decline, (Objective O4), the decline in children with and without PCP can be compared using an unpaired t test or a Wilcoxon rank sum test. More elaborate longitudinal data analyses are described in Section 7.3. To determine whether PCP shortens the life span of HIV-infected children with chronic lung disease (Objective O4), a survival analysis will be performed. Detailed discussion of such an analysis is described in Section 7.4.

All hypotheses and objectives referring to HIV-infected children apply to children in Groups I and IIA.

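### Objective O2 chooses its cut-points and evaluates its marker combinations in the cohort used to report their accuracy, with no validation step, so the reported accuracy will be somewhat too favourable

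*Protocol*

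**What the plan says.** Section 2.3 sets O2 as a secondary objective: "To determine whether pulmonary and cardiovascular disease associated with vertically transmitted HIV infection is detectable with sensitive diagnostic methods before clinical signs and symptoms appear". Section 2 says that secondary objectives matter scientifically as much as the primary hypotheses, and early detection is also the second overall goal in section 2.1.

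Section 7.2 gives the O2 analysis in three consecutive steps:

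- accuracy: "the sensitivity, specificity and positive and negative predictive values of each method will be determined";
- threshold: "In order to determine the optimal cut-point for a diagnostic measure, a receiver operating characteristic (ROC) analysis will be performed (Metz, 1978";
- combinations: "Combinations of diagnostic methods that may better detect disease will be evaluated using logistic regression analysis".

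The section then pairs measures with diseases: LDH or PO2 (or the alveolar-arterial difference) with PCP, IgG with lymphoproliferative lung disease, echocardiographic measures such as fractional shortening with ventricular disease, EKG measures such as the PR interval with arrhythmia, and DTPA with early lung disease. On population it says: "All hypotheses and objectives referring to HIV-infected children apply to children in Groups I and IIA".

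No criterion for an optimal cut-point is named. No second sample, data split, resampling or optimism correction is described.

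**The concern.** LDH, PO2, IgG, fractional shortening and the PR interval are continuous, so their sensitivity, specificity and predictive values exist only at a cut-point. Section 7.2 obtains that cut-point by searching the study's own ROC curve and names one cohort for the whole analysis. A threshold chosen because it separates these particular children well has partly fitted their chance variation, so its accuracy in the same children overstates its accuracy in new ones. The same holds for a logistic score whose coefficients were estimated on the children it is scored on.

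O2 is where the study says whether surveillance tests can find disease early. Overstated accuracy would carry into recommendations on which tests and thresholds to use. The 1% level that section 7.1 adopts for multiple comparisons does not help: it concerns hypothesis tests, and this is bias in an estimate.

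**Working it through.** The protocol states no accuracy, precision or sample-size figure for O2, so there is no figure of its own to reproduce. The size of the bias was found by simulation.

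**Inputs from the protocol**

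- Section 4.2: "An estimated 200 Group I and an estimated 600 Group II subjects are expected to be entered into the study", and "it is expected that 120 Group IIa (HIV-positive) subjects will ultimately be diagnosed as positive". HIV-infected children: 200 + 120 = 320.
- Table 6: PCP 24%, lymphoproliferative lung disease 16%.
- Cases among 320: 0.24 × 320 = 76.8, taken as 77; 0.16 × 320 = 51.2, taken as 51.
- Cases if only Group IIa were analysed: 0.24 × 120 = 28.8, taken as 29; 0.16 × 120 = 19.2, taken as 19.

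**Assumptions not in the protocol**

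- The optimal cut-point is the one that maximises the Youden index J = sensitivity + specificity - 1.
- Each child contributes one value, and the direction of the marker is known in advance.
- Marker values are N(0,1) in non-cases and N(d,1) in cases.

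**Formulas**

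- AUC = Φ(d/√2). AUC 0.5 gives d = 0; AUC 0.75 gives d = √2 × Φ⁻¹(0.75) = 0.95.
- Apparent J is the maximum over c of the sample value of sensitivity(c) + specificity(c) - 1.
- True J at the chosen c is Φ(d - c) - Φ(-c).
- Optimism is mean apparent J minus mean true J.

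**Results (2,000 runs per row)**

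| Children | Cases | True AUC | Apparent J | True J at chosen cut-point | Optimism |
|---|---|---|---|---|---|
| 320 | 77 | 0.75 | 0.407 | 0.354 | 0.053 |
| 320 | 51 | 0.75 | 0.418 | 0.351 | 0.067 |
| 120 | 29 | 0.75 | 0.441 | 0.345 | 0.096 |
| 120 | 19 | 0.75 | 0.455 | 0.340 | 0.115 |
| 320 | 77 | 0.50 | 0.081 | 0.000 | 0.081 |
| 320 | 51 | 0.50 | 0.092 | 0.000 | 0.092 |
| 120 | 29 | 0.50 | 0.125 | 0.000 | 0.125 |
| 120 | 19 | 0.50 | 0.148 | 0.000 | 0.148 |

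A repeat with 10,000 runs gave optimism of 0.053, 0.065, 0.095 and 0.114 for the four AUC 0.75 rows.

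**What a null marker looks like at 320 children.** In a separate set of 4,000 runs, the mean apparent sensitivity and specificity were 56% and 52% with 77 cases, and 58% and 51% with 51 cases. The apparent positive predictive value was 30% against a prevalence of 24%, and 21% against 16%; for a null marker it should equal the prevalence.

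**Where the bias grows**

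- Rarer outcome: with 6% of 320 affected (19 cases), the apparent J of a single null marker is 0.14.
- Combination: two independent null markers in a logistic score, 77 cases among 320, give an apparent J of 0.13, against 0.08 for one marker.

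**The case against.** The strongest reply is that this rests on silence. Section 7.2 does not say in so many words that accuracy will be read at the chosen cut-point in the same children, and internal validation of a secondary diagnostic objective could sit in an analysis plan that is not shown. That is fair as far as it goes, and a later plan could supply the correction. But section 7.2 opens by presenting itself as the account of the specific methods for each objective. It commits O2 to a data-chosen cut-point and names one cohort. Carried out as written, that method gives biased figures, so the point concerns a stated method and not only a missing detail.

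The reply also notes that some limits come from outside the ROC step: blood-gas normal values and SpO2 bands (section 5.2.4.3), echocardiographic comparison with 250 normal subjects and a stress-velocity limit of -1.96 (section 5.3.3), and fractional shortening below 20% (section 5.3.7). This is correct and makes the fix easier, but section 7.2 does not tie O2 to any of them.

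A reader might infer several stronger things that the documents do not support:

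- That a worthless test would look useful. At 320 children a single null marker shows sensitivity and specificity only slightly above one half, which nobody would take for a good test.
- That false-positive rates are multiplied. No significance test at the chosen cut-point is planned for O2.
- That a large multi-marker model will be badly overfitted. Section 7.2 assigns the markers to different diseases and describes no model containing all of them.
- That the plan picks the best combination. It says only that combinations will be evaluated.
- That the 120-child figures describe the plan. They apply only if Group IIa is analysed alone, which is not stated for O2.

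**Conclusion.** The concern holds in a limited form. Followed as written, section 7.2 will report optimistic sensitivity, specificity and predictive values for O2. For a useful single marker (true AUC 0.75) and the two main lung outcomes, the overstatement of sensitivity + specificity - 1 is about 0.05 to 0.07 at the planned 320 children, and about 0.09 to 0.12 if only 120 are analysed. It is larger for rare outcomes, small subgroups and combinations. The AUC of a single marker is not biased by choosing a cut-point.

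These sizes depend on the Youden criterion, normal marker values, one value per child and a known direction; another optimality criterion would change them. Using the same children for selection and reporting is the natural reading of a one-cohort plan, though it is not stated outright. This is a cheap improvement, not a flaw that undermines the study.

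**What to change.** Add to section 7.2, under O2:

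1. Where the protocol already states a limit for a measure, such as fractional shortening in section 5.3.7 or the arterial oxygen values in section 5.2.4.3, report accuracy at that limit, declared as the analysis threshold before the data are examined.
2. For any cut-point chosen from the data, and for any logistic combination, report cross-validated or bootstrap optimism-corrected sensitivity, specificity, PPV and NPV, repeating the cut-point search or model selection in every resample. Leaving out one of the five centers at a time would be a natural cross-validation scheme.
3. Name the criterion that makes a cut-point optimal.

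The cost is slightly more analysis work and slightly less favourable reported accuracy. No new data or children are needed.

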7.3 Longitudinal Analyses

Various clinical and laboratory measurements will be made periodically during the 2-1/2 to 4-1/2 year follow-up period. Most longitudinal methods typically require balanced data (i.e., no missing observations) which is unlikely to be true in this study. Alternatively, meaningful summaries of the longitudinal experience for each patient will be developed such as the rate of change from baseline, and these summary measures can be compared between groups using t tests or Wilcoxon rank sum tests.

Changes in continuous measurements (e.g., PaO₂) over time will be compared by calculating a slope over time for each patient and comparing mean slopes between groups. The validity of the linearity assumption will be investigated. Due to varying lengths of follow-up caused by staggered enrollment, termination of the study, dropouts, and mortality, there will be different numbers of measurements between subjects and inequalities in the precision of estimates of individual slopes, so a weighted mean slope will be used to determine group means and variances. These weighted mean slopes can be compared between groups using a weighted regression model which can also include covariates from baseline.

The missing data problem may require more sophisticated data analysis approaches. Fortunately, much recent work in the analysis of longitudinal data with missing values has been done. In October, 1986, the NHLBI held a workshop on "Methods for Long-term Data Analysis in Epidemiological and Clinical Studies." All the papers presented at this workshop have been published as Volume 7, 1988, Statistics in Medicine. In addition, a review of statistical methods for longitudinal data has been given by Cook and Ware (1983) in which analysis approaches for continuous and dichotomous data are discussed. Also, a discussion of linear model approaches for the analysis of longitudinal studies has been given by Ware (1985). A unified approach useful for modeling continuous or categorical longitudinal data has been developed by Liang and Zeger (1986) using a generalized estimating equations approach. In addition, Schluchter has developed methodology to analyze continuous repeated measures data when the covariance structure is specified (Jennrich and Schluchter, 1986; Schluchter, 1988). The disadvantage of all these methods is that missing observations are assumed to be missing at random, i.e., not related to the process being studied. For example, if mortality during the study is related to a subject's rate of decline of CD4/CD8 ratio, then the values of CD4/CD8 ratio that are missing because that subject died during the study are not missing at random. This type of nonrandom missingness has been termed "informative censoring" (Wu and Carroll 1988). At present, there are only a few models available to handle informatively censored longitudinal data. The Wu and Carroll (1988), method uses a random effects linear model where the missing process is modelled assuming a probit function that allows tractable estimation, Wu and Bailey (1988), consider simpler ad hoc noniterative techniques for handling informatively censored data, and Wu and Bailey (1989) propose a general linear models approach.

7.4 Analyses of Time-To-Event Data

Survival (time-to-event) analysis methods will be used to analyze morbidity and mortality outcomes and to identify prognostic factors for each event (e.g., HIV infection). Kaplan-Meier (Kaplan and Meier, 1958) estimates of "survival" curves will be obtained for each subgroup of interest. The construction of confidence interval estimates around a point of the survival curve will use the estimate of standard error suggested by Peto, Pike, et al (1977). Comparisons between subgroups (e.g., those children with and without confirmed HIV infection) will be made using the Mantel-Haenszel test (Mantel, 1966). These methods are useful in that they allow for varying length of follow-up and permit the comparison of the entire survival experience during the follow-up period. Kaplan-Meier estimates of time to determination of HIV infection will be developed for children in Group II.

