5.4 Pathological Studies: Postmortem Examination of HIV-Infected Infants in Groups I and II

A number of infants and children in the study population will die each year. It is estimated that at least 50% of the P²C² HIV study patients who die will come to autopsy. Postmortem examination will provide important morphologic correlation with the antemortem functional assessments and clinical indicators. Consent for autopsy will be obtained in the customary manner for each institution using their standard hospital autopsy consent form. In those cases in which permission is obtained, the autopsy will be done in a timely fashion, generally within 24 hours of the demise of the patient. If there are no restrictions made in the consent given, a complete autopsy will be performed. A standard protocol will be used to ensure that appropriate cultures are performed, and that appropriate tissue is sampled and preserved for light microscopy, electron microscopy, and other special studies that may be done as ancillary studies.

[figure not shown]
The lungs will be prepared in a standard fashion by inflation fixation so that they will be suitable for morphometric assessment for correlation with clinical studies of pulmonary function as an ancillary study.

The heart will be carefully examined for structural malformations, chamber dimensions, ventricular wall and valve measurements according to a standard protocol so that appropriate tissues are retained for examination and ancillary studies.

Lesions of small and medium sized arteries have been described in the brain, kidneys, lungs, spleen, skeletal muscle, thymus, and small intestine. The brain was consistently involved. Apparently, larger musculoelastic arteries are not affected; however, it is not clear which such vessels have been examined in published reports. No arterial lesion was identified on gross examination and none could be seen radiologically. In order to examine the incidence and extent of arterial involvement in pediatric AIDS, arteries from various sites will be systematically examined in addition to evaluation of intraparenchymal vascular branches within the various organs.

Figure 8

EVALUATION OF PATIENTS WITH POSSIBLE SYMPTOMS RELATED TO THE HEART

6. Distributed Data Entry and Data Management

Figures 5 and 6 diagram the computer communication network, flow of study data, respectively. Various components of this system are described in detail in the following sections.

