7.1 Introduction

Since the sample for this study will not be a random sample from a general population, a description will be prepared of the baseline variables of the subjects enrolled into each of the Groups I and II: (I) Infants and children with symptomatic HIV-infection, (II) Newborn infants of mothers entered into the study in whom HIV antibody tests were positive during pregnancy. Group II will also be split into Groups IIa and IIb based upon the child's own confirmed HIV status. Such a description will help to characterize these subjects. The variables considered in such a description could be categorized as follows: (1) demographic characteristics, (2) mothers' medical history, (3) cardiac data, (4) pulmonary data, and (5) immunological and infectious disease data. The description will include medians and confidence intervals on means and proportions.

The general approach to the analysis will be one that concentrates on a better understanding of the "natural" history of pediatric HIV infection. Although some of the analyses to be performed for this study will involve tests of hypotheses, (e.g., comparison of HIV-positive and HIV-negative children), several of the objectives of the study relate to questions of estimation within groups. For example, estimation of the incidence of HIV-infection in Group II and of various complications in Groups I, IIa and IIb will be obtained as well as their associated confidence intervals. It is also important to keep in mind that many comparisons and confidence intervals are to be made. Therefore, multiple comparisons may yield a significant result due to chance alone. While testing hypotheses at the 1% significance level will help to adjust for this, the magnitude of differences will also be examined.

A problem that may arise with this population is incomplete data and timing of follow-up visits. Also, the exact time points when events (HIV infection, complications, etc.) occur may not be known. Primary outcome variables may be the development of: HIV infection in Group II, major complications such as left ventricular dysfunction, PCP and lymphoproliferative lung disease, and death (although the rate may be low given the relatively short follow-up period of the study). Survival (time-to-event) analysis will be the primary type of analysis to be used.

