7.2 Statistical Methods

Specific statistical methods that will be used to evaluate each primary and secondary hypothesis or objective are described in this section.

The incidence, prevalence and recurrence rates of cardiac and lung complications (Objectives O1 and O3) will be summarized using confidence intervals on proportions. These rates will be determined at various time points (e.g., fetus, neonate and age 2.5 years); and will also be calculated in various subgroups such as Groups IIA and IIB or those children with and without certain cofactors (e.g., receiving drugs for treatment of HIV virus).

The primary hypotheses (H1 and H2) of comparing complication rates at specific time points in children with and without HIV-infection (Groups IIA and IIB) will be evaluated using the Mantel-Haenszel chi-square test stratifying on important potentially confounding variables such as IVDA of the mother. If there are several factors that need to be adjusted for simultaneously, a logistic regression analysis will be used to compare the rates with the factors as independent variables in the model along with an indicator variable representing group assignment. Similar analyses also apply to Hypotheses H3 and H4.

The persistence of cardiac abnormalities from the fetus to the neonate (Hypothesis H5) can be evaluated using McNemar's chi-square. If the abnormality is measured using a continuous variable (e.g., wall thickness from an echocardiogram), a paired t test or Wilcoxon signed rank test can be used.

To determine which cofactors are associated with cardiac or pulmonary abnormalities (Hypotheses H6 and H7), a logistic regression analysis will be done.

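### Section 7.4 prescribes Kaplan-Meier curves for non-fatal complications without treating prior death as a competing event

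*Protocol*

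**What the plan says.** Section 7.1 lists possible primary outcomes: HIV infection in Group II, major complications (left ventricular dysfunction, PCP and lymphoproliferative lung disease are the examples), and death. It then says: "Survival (time-to-event) analysis will be the primary type of analysis to be used".

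Section 7.4 covers fatal and non-fatal events together: "Survival (time-to-event) analysis methods will be used to analyze morbidity and mortality outcomes and to identify prognostic factors for each event". Kaplan-Meier "estimates of 'survival' curves will be obtained for each subgroup of interest", with confidence intervals at points on the curve, Mantel-Haenszel (log-rank) comparisons and Cox models. It contains no rule for a death that comes before the complication, and no competing-risk estimator.

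Section 7.2 gives a second route to complication frequency: "The incidence, prevalence and recurrence rates of cardiac and lung complications (Objectives O1 and O3) will be summarized using confidence intervals on proportions". It says that the primary hypotheses H1 and H2 "will be evaluated using the Mantel-Haenszel chi-square test stratifying on important potentially confounding variables", or by logistic regression, on rates at specific time points.

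On mortality, Section 7.1 includes among the outcomes "death (although the rate may be low given the relatively short follow-up period of the study", while Section 5.4 says: "A number of infants and children in the study population will die each year". No death rate is given. Section 7.3 does recognise that death can be informative, with an example that begins "if mortality during the study is related to a subject's rate of decline of CD4/CD8 ratio", but it applies this only to repeated measurements.

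**The concern.** A Kaplan-Meier analysis knows two states, event and censored. If the event is a complication and a child dies without it, censoring that child treats them as still able to develop it, at the rate seen in the survivors. One minus the curve then describes a population in which nobody dies. The study's overall goals (Section 2.1) ask for something else: how often these disorders occur in children with HIV, some of whom die first.

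The two quantities differ only if children die complication-free. When they do, one minus Kaplan-Meier is always the higher, and the gap grows with mortality and with time. At stake is the level of any complication curve reported from Section 7.4, chiefly in Groups I and IIa, and the visual comparison of curves between subgroups with different mortality.

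Sections 7.1 and 7.4 together also point to curves as the primary analysis, while Section 7.2 points to proportions. The protocol does not say which figure is to be read as the complication frequency.

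**Working it through.** **1. The plan's own precision figure.** Section 4.2.2 gives the half-width as 100 × 1.96 × √(p(1−p)/n).
- p = 0.25, n = 200: 6.0 points, as stated.
- p = 0.50, n = 200: 6.9 points, as stated.
- p = 0.24, n = 200: 5.9 points. With n = 120 (expected Group IIa): 7.6 points.

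These are calculations on simple proportions, as is Table 7. Neither uses a Kaplan-Meier curve, so neither changes.

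**2. Inputs for the check.**
- Illustrative true incidence: 24%, the PCP rate in Table 6. That table gives it for all ages, with no time horizon. Attaching it to 3 or 5 years is an assumption made here.
- Time points: 3 years, the minimum for Group II under Appendix 1 (recruitment to 31 January 1994, follow-up to 31 January 1997), and 5 years, inside the 6 2/3-year maximum there. Section 7.3 still cites 2.5 to 4.5 years.
- Death rate: not in the protocol. Hazards of 2%, 5% and 10% per year are assumed, constant over time, in children without the complication.

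**3. Formulas.** With complication hazard c, death hazard d and time T:
- cumulative incidence with death competing = c/(c+d) × [1 − exp(−(c+d)T)]
- one minus Kaplan-Meier with deaths censored = 1 − exp(−cT)

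Set the first to 0.24, solve for c, and put c into the second.

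**4. One case in full (T = 5, d = 0.05).** The solution is c = 0.0628. Check: 0.0628/0.1128 × [1 − exp(−0.564)] = 0.5567 × 0.4311 = 0.240. Then 1 − exp(−0.314) = 0.269, so a true 24% reads 26.9%.

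**5. Results for a true 24%.**

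| Time | Death rate per year | 1 − exp(−dT) | 1 − Kaplan-Meier | Excess (points) |
|---|---|---|---|---|
| 3 years | 2% | 5.8% | 24.7% | 0.7 |
| 3 years | 5% | 13.9% | 25.7% | 1.7 |
| 5 years | 2% | 9.5% | 25.2% | 1.2 |
| 5 years | 5% | 22.1% | 26.9% | 2.9 |
| 5 years | 10% | 39.3% | about 30% | about 6 |

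The third column is the mortality by that time that each assumed rate implies in the absence of the complication.

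**6. Reading.** At 2% to 5% per year the excess is 0.7 to 2.9 points, well inside the half-width of about 6 points at n = 200. It matches that half-width only at about 10% per year over 5 years. Unlike sampling error, it always runs upward and does not shrink as n grows.

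**The case against.** **Incidence is assigned to proportions.** Section 7.2 places the incidence, prevalence and recurrence rates (O1, O3) on proportions with confidence intervals, and Section 4.2.2 plans precision on that basis. Section 7.4 nowhere says that one minus Kaplan-Meier will be reported as incidence. This stands. A reader might infer that all complication incidence will come from Kaplan-Meier curves. The protocol does not support that.

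**No specified test is biased.** A reader might also infer that the IIa versus IIb comparison is distorted. H1 and H2 are tested on rates at specific time points by Mantel-Haenszel chi-square or logistic regression. The log-rank and Cox analyses in Section 7.4 remain valid comparisons of cause-specific hazards when deaths are censored. This too stands. What can mislead is the height of the curves.

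**Censoring at death is not stated.** It is the default, but the text would also allow death to count as part of a composite event, and such rules are often left to a statistical analysis plan. This stands in part. The protocol has itself fixed Kaplan-Meier for morbidity, and that estimator offers only those two treatments of death. Neither gives the cumulative incidence of the complication when some children die first.

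**Mortality may be low.** Section 7.1 says so, and a 10% yearly rate would mean about 39% dead by 5 years in the absence of the complication, which the protocol does not support. It is fair that the size cannot be asserted. However, the remark rests on a short follow-up period, Appendix 1 now extends follow-up to January 1997, and Section 5.4 expects deaths every year.

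**Conclusion.** The point holds in a limited form. Sections 7.1 and 7.4 choose Kaplan-Meier for non-fatal complications, call time-to-event analysis the primary type, and make no provision for prior death, although Section 7.3 treats death as informative for repeated measurements. If deaths are censored, the complement of each complication curve overstates cumulative incidence.

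The size depends on a death rate that the protocol does not give. For an illustrative true 24%, the excess is about 1 to 3 points for death rates of 2% to 5% per year over 3 to 5 years, and about 6 points at 10% per year over 5 years. This assumes constant hazards and a time horizon that Table 6 does not state. An unconditional claim that complication rates in infected children will be overstated goes beyond the documents.

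Survival curves for death itself are unaffected, as are the analyses in Section 7.2, Table 7 and the hazard comparisons. This is a cheap improvement to the analysis, not a flaw in the design.

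**What to change.** In Section 7.4:
- Estimate time-to-complication curves by the cumulative incidence function (Aalen-Johansen), with death before the complication as a competing event.
- Keep Kaplan-Meier for death and for complication-free survival, where death counts as an event.
- Keep the log-rank and Cox analyses, and label their results for non-fatal complications as cause-specific.

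In Section 7.1 or 7.2, state whether the proportions or the time-to-event curves are the headline estimate of complication frequency.

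The cost is revised wording and a little more analysis work. No new data are needed, because Section 7.1 already commits to finding out whether children lost to follow-up are alive. Reported rates will be slightly lower than one minus Kaplan-Meier would have shown.
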